APPENDIX 4. DLT CRITERIA

GENERAL PRINCIPLES

A TEAE will be declared as DLT if both of the following criteria are met:

1. The TEAE occurred after the start of infusion in cycle 1 of Part 1.
 - a. If a TEAE that fulfills a DLT criterion is observed in cycle ≥ 2 of Part 1, then the sponsor may declare this event a DLT after consultation with the investigator(s).
2. The TEAE is at least possibly related to MT-3724, as determined by the sponsor after consultation with the investigator(s).

Note: TEAEs related to LEN will not be declared a DLT unless they exceed in severity the worst grade described or are not mentioned in the reference prescribing information. If a Grade ≥ 3 TEAE related to LEN is more severe than the worst grade described in the reference prescribing information or has not been reported in the reference prescribing information, then the sponsor may declare this event a DLT after consultation with the investigator(s).

The severity of TEAEs potentially fulfilling the DLT criteria will be graded according to the CTCAE v.5.0.

POTENTIALLY QUALIFYING TEAEs: Any TEAE listed below may represent a DLT for MT-3724 in this study.

Hematological TEAEs

- Grade ≥ 3 febrile neutropenia (ANC $<1000/\mu\text{l}$ and a single body temperature reading of $>38.3^\circ\text{C}$ (101°F) or a sustained body temperature of $\geq 38.0^\circ\text{C}$ (100.4°F) for more than 1 hour)
- Grade 4 neutropenia (ANC $<500/\mu\text{l}$) for >5 days; if the investigator determines that G-CSF therapy for Grade 4 neutropenia is essential within ≤ 5 days of onset, then this AE will also qualify as DLT
- Grade 3 thrombocytopenia ($<50,000/\mu\text{l}$ and $\geq 25,000/\mu\text{l}$) with clinically significant bleeding (i.e., bleeding requiring platelet transfusion)
- Grade 4 thrombocytopenia ($<25,000/\mu\text{l}$) with or without bleeding
- Grade 4 anemia

Nonhematological TEAEs

- Grade ≥ 2 Cytokine Release Syndrome
- Grade ≥ 3 Capillary Leak Syndrome
- Grade ≥ 3 acute kidney injury
- AST and/or ALT increase >5.0 times ULN (>8.0 times for those with liver involvement)
- AST and/or ALT increase >3.0 times ULN with concomitant increase in total bilirubin ≥ 2.5 times ULN
- Total bilirubin >4.0 times ULN

Note: for AST, ALT and bilirubin the investigator in consultation with the Medical Monitor and the sponsor should diligently assess if the value above either 5.0, 3.0 or 1.5 x ULN (depending on laboratory values as specified above), could be interpreted as non-DLT in light of the elevated baseline value (see CTCAE v5.0) and liver involvement.

- Grade ≥ 3 infusion-related reaction or other Grade ≥ 3 hypersensitivity reaction
- Any Grade ≥ 3 electrolyte abnormality that does not resolve, with or without intervention, to Grade <2 within 72 hours.
- Any other Grade ≥ 3 nonhematological toxicity **excluding** the following:
 - Nausea, vomiting, or diarrhea, if manageable with antiemetic or antidiarrheal agents within 7 days of onset
 - Fatigue lasting ≤ 72 hours
 - Grade 3 laboratory abnormalities, if asymptomatic and without a clear clinical correlate, as determined by the sponsor after consultation with investigator(s).
- Any other toxicity at least possibly related to MT-3724, irrespective of the type or severity, that would qualify as DLT, as determined by the sponsor after consultation with investigator, considering the severity, duration, poor response to remedial therapy and/or inadequate resolution. This may be Grade 1 or Grade 2 toxicity that notably limits the activities of daily life to the extent that makes dose reduction necessary to ensure subject's compliance (e.g., long-lasting fatigue or anorexia).

APPENDIX 5. COCKCROFT-GAULT (2009)

Creatinine clearance should be calculated using the Cockcroft-Gault Formula ([Cockcroft DW 1979](#)), which is given below:

$$\text{CLcr} = \{((140 - \text{age}) \times \text{weight}) / (72 \times \text{SCr})\} \times 0.85 \text{ (if female)}$$

Abbreviations/Units: CLcr (creatinine clearance) = mL/minute; Age = years; sCr (serum creatinine) = $\mu\text{mol/L}$

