⁴ Prior medication is any medication (prescription, OTC and supplements) used within 4 weeks prior to the start of treatment. Prior therapy for NHL should be captured separately from prior medications.

⁵ Prior systemic therapy for NHL (including SCT) administered at any time before the start of treatment should be documented by itemizing each regimen (line of treatment) and the individual agents within each regimen. The date of last CD20-based therapy should also be documented in the CRF.

⁶ Prior radiotherapy for NHL administered at any time before the start of treatment.

⁷ Blood pressure (systolic and diastolic), heart rate and respiratory rate should be measured after 5-10 minutes of quiet rest in a sitting or semi-recumbent position.

⁸ When ECG and blood pressure assessments are scheduled to occur at the same time point, then the ECG should be performed first and the blood pressure/heart rate measurement may begin immediately after ECG recording (without additional 5-10 minutes' rest).

⁹ Triplicate 12-lead ECG should be obtained as three standard ECGs recorded in close succession and not more than 2 minutes apart. The subject must rest quietly in supine or semi-recumbent position for 5-10 minutes before and during the procedure.

¹⁰ A scan of all anatomic regions involved with the measurable disease by PET-CT (in subjects with FDG-avid tumor histology) or CT/MRI (in subjects with tumor histology of low or variable FDG avidity). CT of diagnostic quality should be collected for all subjects at baseline, whenever possible.

¹¹ Screening (baseline) radiological tumor assessments should be obtained as close to the start of treatment as possible, and within 28 days of C1D1.

¹² Done at Screening (within 1 month before starting study treatment). A pre-study LVEF assessment is acceptable if obtained within 6 months before screening and at least 28 days after the last cancer therapy provided the subject has not received any potentially cardiotoxic agents since then.

¹³ It is recommended to assess RTX serum concentration prior to performing other screening procedures.

¹⁴ Calculated by the central laboratory using the Cockcroft-Gault equation and the serum creatinine from the corresponding chemistry panel.

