4.1 Inclusion criteria

Subjects must meet ALL the following criteria to be eligible for the study.

1. Be adequately informed about the study and fully consent to participation as demonstrated by signing the written ICF before any screening procedure.
2. Be aged ≥ 18 years on the date of signing the informed consent form.
3. Have relapsed or refractory CD20-positive B-cell NHL that, in the investigator's opinion, could benefit from MT-3724+LEN therapy. Subjects must have proof of CD20-positive NHL, either by:
 - a. Historical biopsies (obtained with diagnosis of relapsed or refractory disease), or
 - b. Fresh biopsies.
 - c. Bone marrow biopsy, excisional lymph node biopsy, and core biopsy of any involved organ are all acceptable methods; FNA are not acceptable.
4. All subtypes of B-cell NHL may be considered for Part 1 (MT-3724 Dose Escalation). Only histologically documented DLBCL (including mixed histology) may be considered for Part 2 (MTD Expansion Cohort).
5. Have received all available approved therapies for NHL, one of which should be anti-CD20-based therapy.
 - a. Subjects whose prior therapy includes chimeric antigen receptor t-cell (CAR-T) cell therapy are eligible.
 - b. Subjects who underwent stem cell transplant (SCT) >100 days for autologous SCT or >180 days for allogeneic SCT before study drug administration and exhibited a full hematological recovery (consistent with the existing inclusion criteria requirements and without PRBC or platelet transfusions within 2 weeks of C1D1) prior to relapse are eligible.
 - c. Subjects who have been ineligible for approved therapies in the opinion of the investigator, or have refused such therapies, may be eligible at the investigator's discretion, upon sponsor approval.
6. Have bi-dimensionally measurable disease by Lugano Classification for NHL.
 - a. >1.5 cm LD_i for lymph nodes
 - b. >1.0 cm LD_i for extranodal disease
7. Have Eastern Cooperative Oncology Group (ECOG) performance status of ≤ 2 ([Appendix 6](#)).

8. Have adequate bone marrow function, as determined by all the following:
 - a. Absolute neutrophil count (ANC) $\geq 1,000/\text{mm}^3$
 - b. Platelet count $\geq 50,000 \text{ mm}^3$
 - c. Hemoglobin $\geq 8.0\text{g/dL}$
9. Have adequate kidney function, CLcr to be $\geq 50 \text{ mL/min}$ either measured or estimated using the Cockcroft-Gault formula ([Appendix 5](#)).

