 - a. At the investigator's discretion, the eGFR result $<50 \text{ mL/min}$ may be verified by measurement of CLcr based on the 24-hour urine collection. Subjects with CLcr $\geq 50 \text{ mL/min}$ will be eligible irrespective of the eGFR result.
10. Have adequate hepatic function, as determined by:
 - a. Total bilirubin $<1.5 \times \text{ULN}$, or direct bilirubin $<1.5 \times \text{ULN}$ for subjects with elevated total bilirubin secondary to Gilbert's Syndrome, and
 - b. Aspartate aminotransferase $\leq 3.0 \times \text{ULN}$ (or $\leq 5 \times \text{ULN}$ if liver involvement), and
 - c. Alanine aminotransferase $\leq 3.0 \times \text{ULN}$ (or $\leq 5 \times \text{ULN}$ if liver involvement).
11. Have adequate coagulation, as determined by:
 - a. International normalized ratio or PT $\leq 1.5 \times \text{ULN}$ (unless on therapeutic anticoagulants)
 - b. Activated partial thromoplastin time $\leq 1.5 \times \text{ULN}$ (unless on therapeutic anticoagulants)
12. Albumin $\geq 3.0 \text{ g/dL}$.
13. Women of reproductive potential must have a negative pregnancy test on 2 occasions during the screening period (within 10-14 days and within 24 hours before the start of treatment). Women not of reproductive potential are female subjects who are postmenopausal (>1 year since last menstrual cycle) or permanently sterilized (e.g., hysterectomy, bilateral salpingectomy).
14. Males must agree to always use a latex or synthetic condom during any sexual contact with females of reproductive potential while taking LEN and for up to 4 weeks after discontinuing LEN, even if they have undergone a successful vasectomy. Male subjects taking LEN must not donate sperm.
15. Subjects of reproductive potential and their partners must agree to either abstain continuously from heterosexual intercourse or to use 2 methods of reliable birth control simultaneously to begin 4 weeks prior to initiating treatment with LEN until 28 days after the last dose of MT-3724 or LEN. The investigator or a designated associate should advise the subject how to achieve adequate contraception. The following birth control methods may be considered: one highly effective form of contraception – tubal ligation, IUD, hormonal (birth control pills, injections, hormonal patches, vaginal rings, or implants), or partner's vasectomy, and one additional effective contraceptive method – male latex or synthetic condom, diaphragm, or cervical cap.

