6.4.2 Estimated glomerular filtration rate

The eGFR will be assessed as a measure of renal function and will be calculated using the Cockcroft-Gault creatinine equation ([Appendix 5](#)).

The eGFR will be derived from the serum creatinine values obtained from the blood chemistry assessment at all time points listed above ([Section 6.4.1](#)).

At the investigator's discretion, the eGFR results at screening that fall outside the limit required for eligibility may be verified by the formal measurement of CLcr based on the 24-hour urine collection. Furthermore, if warranted by the eGFR result at any other time point, the investigator may order CLcr (measured from the 24-hour urine) as an unscheduled assessment.

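### Appendix 5 pairs the Cockcroft-Gault constant 72 with serum creatinine in µmol/L, so the printed estimate is 88.4 times too low and no realistic subject reaches the 50 mL/min limit by it

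*Protocol*

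**What the plan says.** Protocol Appendix 5 gives creatinine clearance as (140 − age) × weight, divided by 72 × serum creatinine, times 0.85 for women. Its unit line begins "Abbreviations/Units: CLcr (creatinine clearance) = mL/minute; Age = years; sCr (serum creatinine", and the creatinine entry continues as "sCr (serum creatinine) = $\mu\text{mol/L", that is, creatinine in µmol/L. It prints no conversion factor and no unit for weight.

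The formula is used in these places:

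- **Inclusion criterion 9 (Protocol Section 4.1 and synopsis)** requires a clearance of at least 50 mL/min, "either measured or estimated using the Cockcroft-Gault formula", and points to Appendix 5.
- **Criterion 9a** says that a low estimate "may be verified by measurement of CLcr based on the 24-hour urine collection", at the investigator's discretion. A subject whose clearance is at least 50 mL/min "will be eligible irrespective of the eGFR result".
- **Table 2, footnote 14** says how the screening eGFR is obtained: "Calculated by the central laboratory using the Cockcroft-Gault equation and the serum creatinine from the corresponding chemistry panel".
- **Section 6.4.2** refers to Appendix 5 for the equation and extends it beyond screening: "The eGFR will be derived from the serum creatinine values obtained from the blood chemistry assessment at all time points listed above". The laboratory panel in Appendix 1 also refers to Appendix 5 for eGFR.

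**The concern.** A formula with the constant 72 gives mL/min only if creatinine is in mg/dL and weight in kg. With creatinine in µmol/L the denominator is nearly ninety times too large, and an ordinary adult gets a clearance near 1 mL/min. That cannot be the scale on which a limit of 50 mL/min was set.

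Two things are at stake. The first is the eligibility decision under criterion 9, where a literal reader would find every estimate far below the limit. The second is the comparability of eGFR across sites and visits. Someone who notices the problem has to improvise a correction, and different sites may do so differently. Appendix 5 is the only specification of the formula in either document.

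**Working it through.** The documents contain no worked clearance value, so there is no figure to reproduce. The check evaluates the printed formula and compares the result with the protocol's own limit.

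**Inputs from the Protocol:** the formula, the constant 72, the factor 0.85 for women, creatinine in µmol/L and clearance in mL/min (Appendix 5); the limit of 50 mL/min and the minimum age of 18 years (Section 4.1); body weight recorded in kg (Sections 5.1.2 and 6.1.2).

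**Inputs not in the documents (assumptions):** the molar mass of creatinine, 113.12 g/mol; illustrative weights of 60 to 200 kg; illustrative creatinine of 0.4 to 1.0 mg/dL, which is 35.4 to 88.4 µmol/L. Higher creatinine only lowers the estimate, so the upper end of that range does not limit the conclusion.

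**Step 1, conversion.** 1 mg/dL = 10 mg/L = 10/113.12 mmol/L = 0.0884 mmol/L = 88.4 µmol/L. Creatinine enters once, in the denominator, so the error is a constant factor of 88.4.

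**Step 2, examples.**

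| Subject | Creatinine | Formula with µmol/L (as printed) | Formula with mg/dL |
|---|---|---|---|
| Male, 65 y, 70 kg | 88.4 µmol/L = 1.0 mg/dL | 75 × 70 / (72 × 88.4) = 0.82 | 75 × 70 / (72 × 1.0) = 72.9 |
| Male, 40 y, 80 kg | 70.7 µmol/L = 0.8 mg/dL | 100 × 80 / (72 × 70.7) = 1.57 | 138.9 |
| Female, 65 y, 70 kg | 79.6 µmol/L = 0.9 mg/dL | 0.85 × 75 × 70 / (72 × 79.6) = 0.78 | 68.9 |
| Female, 75 y, 60 kg | 88.4 µmol/L = 1.0 mg/dL | 0.85 × 65 × 60 / (72 × 88.4) = 0.52 | 46.0 |

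With mg/dL the 50 mL/min limit separates these four subjects. With µmol/L all four fall below 2 mL/min.

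**Step 3, the most favourable case.** Male, 18 y, 200 kg, 35.4 µmol/L: 122 × 200 / (72 × 35.4) = 9.6 mL/min, still about a fifth of the limit.

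**Step 4, inversion.** To reach 50 mL/min as printed, creatinine must be at most (140 − age) × weight / (72 × 50):

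- Male, 65 y, 70 kg: 5,250 / 3,600 = 1.46 µmol/L.
- Male, 18 y, 70 kg: 8,540 / 3,600 = 2.37 µmol/L.

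Alternatively, an 18-year-old man with creatinine 40 µmol/L would have to weigh 50 × 72 × 40 / 122 = 1,180 kg.

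**Step 5, direction.** The printed version divides the intended estimate by 88.4, so it can only understate clearance. A subject who passes on the printed estimate would also pass on the intended one.

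**The case against.** The strongest reply is that the slip may never have reached a subject. Table 2 assigns the calculation to the central laboratory, which may use a validated routine with the right unit. A value near 1 mL/min in an ambulatory patient would be noticed at once. No treatment-modification rule printed in Section 5.4 uses an eGFR cut-off. Acute kidney injury as a dose-limiting toxicity is graded by CTCAE, and eGFR otherwise enters only descriptive laboratory summaries. Nothing shows that the MTD decision or the analysis sets depend on Appendix 5.

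Most of that stands and limits the consequence. It does not remove the error. Neither document states the laboratory's unit or constant. Sites can also hold their own creatinine values: Section 6.4.1 calls for local chemistry when central results will not be ready before dosing, and Section 8.1.3 lets local standard-of-care results from before consent serve for screening. The SAP places sites in North America and Europe, so mixed reporting units are foreseeable.

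A reader might infer three stronger things, none of which the documents support:

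- **That no subject is eligible under the protocol.** Criteria 9 and 9a accept a measured clearance of at least 50 mL/min whatever the estimate, and that route does not use the formula.
- **That subjects with poor renal function could be enrolled.** The error runs only towards exclusion (Step 5).
- **That the unit of weight is undefined.** It is missing from Appendix 5 only; Sections 5.1.2 and 6.1.2 give body weight in kg.

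**Conclusion.** The unit in Appendix 5 is wrong for the printed constant, and the estimate is 88.4 times too low. By that estimate no realistic subject meets the 50 mL/min limit, so followed literally the appendix turns a discretionary 24-hour urine measurement into a requirement for every subject. Any eGFR computed literally from the appendix at later chemistry time points would be wrong by the same factor.

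The factor rests only on the molar mass of creatinine. The statement about realistic subjects rests on the assumed ranges of weight and creatinine, and the margin is wide: the extreme case gives 9.6 mL/min against 50.

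The practical effect is conditional on who computed the value and how, which the documents do not show. This is a definite error that should be corrected. It is not evidence that any subject was wrongly enrolled or that any reported eGFR is wrong.

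**What to change.** In Appendix 5, do one of the following:

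- state serum creatinine in mg/dL and weight in kg, keeping the constant 72; or
- keep µmol/L and write the denominator as 72 × (creatinine / 88.4), with weight in kg.

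Then confirm in writing with the central laboratory which unit and constant it uses, and that any site calculator applies the same formula. The 50 mL/min limit is not in question and stays as it is. The cost is a one-line protocol correction and one query to the laboratory and sites; no analysis or sample size changes.

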APPENDIX 6. ECOG PERFORMANCE STATUS

ECOG will be recorded per the investigator's assessment of subject's performance status:

Grade	Description
0	Fully active, able to carry on all pre-disease performance without restriction.
1	Restricted in physically strenuous activity but ambulatory and able to carry out work of a light or sedentary nature (e.g., light housework, office work).
2	Ambulatory and capable of all self-care but unable to carry out any work activities. Up and about more than 50% of waking hours.
3	Capable of only limited self-care, confined to bed or chair more than 50% of waking hours.
4	Completely disabled. Cannot carry on any self-care. Totally confined to bed or chair.
5	Death

APPENDIX 7. NEW YORK HEART ASSOCIATION (NYHA) FUNCTIONAL CLASSIFICATION

The stages of heart failure will be assessed according to the NYHA functional classification system. This system relates symptoms to everyday activities and the subject's quality of life.

NYHA classification

Class	Subject symptoms
Class I (mild)	No limitation of physical activity. Ordinary physical activity does not cause undue fatigue, palpitation, or dyspnea (shortness of breath).
Class II (mild)	Slight limitation of physical activity. Comfortable at rest, but ordinary physical activity results in fatigue, palpitation, or dyspnea.
Class III (moderate)	Marked limitation of physical activity. Comfortable at rest, but less than ordinary activity causes fatigue, palpitation, or dyspnea.
Class IV (severe)	Unable to carry out any physical activity without discomfort. Symptoms of cardiac insufficiency at rest. If any physical activity is undertaken, discomfort is increased.

APPENDIX 8. ABBREVIATIONS

Abbreviation	Definition
5PS	five-point scale
ACVBP	adriamycin, cyclophosphamide, vindesine, bleomycin and prednisone
ADA	anti-drug antibodies
ADCC	antibody-dependent cell-mediated cytotoxicity
ADR	adverse drug reaction
AE	adverse event
ALT	alanine aminotransferase
ANC	absolute neutrophil count
aPTT	activated partial thromboplastin time
AST	aspartate aminotransferase
□-HCG	Beta-human chorionic gonadotropin
BIW	twice weekly
BMI	body mass index
BORR	best overall response rate
BP	blood pressure
°C	Celsius
C	cycle
C1D1	cycle 1 day 1
CDC	complement-dependent cytotoxicity
CFR	Code of Federal Regulations
CHOP	cyclophosphamide (Cytoxan), doxorubicin (Adriamycin), vincristine (Oncovin), and prednisone
CLcr	creatinine clearance
CLS	capillary leak syndrome
Cm	centimeter
CNS	central nervous system
CR	complete response
CRF	case report form
CRO	contract research organization
CRS	cytokine release syndrome
CS	clinically significant
CT	computer tomography
CTCAE	Common Terminology Criteria for Adverse Events

Abbreviation	Definition
DCR	disease control rate
DHAP	dexamethasone, cytosine arabinoside, cisplatin
DLBCL	diffuse large B-cell lymphoma
DLT	d-dose-limiting toxicity
DO R	duration of tumor response
ECG	electrocardiogram
ECHO	echocardiography
ECOG	Eastern Cooperative Oncology Group
eCRF	electronic CRF
EDC	electronic data capture
EoI	end of infusion
EoT	end of treatment
EPOCH	etoposide, prednisolone, vincristine, cyclophosphamide and doxorubicin
°F	Fahrenheit
FDA	Food and Drug Administration
FDG	fluorodeoxyglucose
FL	follicular lymphoma
FLIPI	Follicular Lymphoma International Prognostic Index
FNA	fine needle aspirate
GCP	Good Clinical Practice
GDP	gemcitabine, dexamethasone and cisplatin
G-CSF	granulocyte-colony stimulating factor
HbsAg	hepatitis B surface antigen
HBV	hepatitis B virus
HCV	hepatitis C virus
HIV	human immunodeficiency virus
HSCT	hematopoietic stem cell transplantation
HR	heart rate
IB	Investigator's Brochure
ICE	ifosfamide, carboplatin and etoposide
ICF	informed consent form
ICH	International Conference on Harmonisation
IEC	Independent Ethic Committee
Ig	immunoglobulin

Abbreviation	Definition
IHC	immunohistochemistry
INR	international normalized ratio
IPI	International Prognostic Index
IRB	Institutional Review Board
IRR	infusion-related reactions
IV	intravenous
Kg	kilogram
L	liter
LDi	longest diameter
LDH	lactic dehydrogenase
LEN	Lenalidomide
LTFU	Long-Term Follow Up
LVEF	left ventricular ejection fraction
LYRIC	Lymphoma Response to Immunomodulatory Therapy Criteria
mAb	monoclonal antibody
MedDRA	Medical Dictionary for Regulatory Activities
Mg	milligram
ML	milliliter
mM	millimolar
MM	multiple myeloma
mmHg	millimeter of mercury
mm ³	cubic millimeter
MRI	magnetic resonance imaging
MTD	maximum tolerated dose
MUGA	multiple-gated acquisition
NAb	neutralizing antibody
NCS	not clinically significant
NHL	non-Hodgkin's lymphoma
NSAIDS	non-steroidal anti-inflammatory drugs
NYHA	New York Heart Association
OR	objective tumor response
ORR	objective tumor response rate
OS	overall survival
OTC	over the counter

Abbreviation	Definition
PCR	polymerase chain reaction
PD	pharmacodynamics
PE	physical examination
PET	positron emission tomography
PFS	progression-free survival
PK	pharmacokinetics
PO	orally
PR	partial response
PRBC	packed red blood cells
PT	prothrombin time
PTT	partial thromboplastin time
Qd	once daily
QTcF	QT interval corrected according to Fridericia's formula
R ²	lenalidomide plus rituximab
RBC	red blood cell (count)
R-CHOP	rituximab-CHOP
REMS	Risk Evaluation and Mitigation Strategy
RNA	ribonucleic acid
RR	respiratory rate
R/R	relapsed or refractory
RTX	rituximab
SAE	serious adverse event
SAP	statistical analysis plan
scFv	single chain variable fragment
SCT	stem cell transplantation
SD	stable disease
STFU	Short-Term Follow-Up
SOC	standard of care
SUSAR	suspected, unexpected serious adverse reaction
TEAE	treatment emergent adverse event
TESAE	treatment-emergent serious adverse events
TIW	three times a week
TSH	thyroid-stimulating hormone
μg	microgram

Abbreviation	Definition
ULN	upper limit normal
WBC	white blood cell (count)

